### **11.2.3. Adverse Event of Interest**

Musculoskeletal pain occurring up to 24 hours post administration of MGTA-145, regardless of severity or relationship to study drug, will be captured as an AE of interest. The severity (based on CTCAE version 5.0), time of onset, duration of back pain, relationship to study drug, outcome, action taken regarding study drug, and any treatment administered will be captured in the electronic data capture (EDC) system.

#### 11.2.4. Serious Adverse Event

A SAE is defined as any appearance of or worsening of any pre-existing undesirable sign(s), symptom(s), or medical conditions(s), which meets any one of the following criteria:

- Is fatal
- Is life-threatening
- Results in persistent or significant disability/incapacity
- Constitutes a congenital anomaly/birth defect
- Requires inpatient hospitalization or prolongation of existing hospitalization, except:
  - Routine treatment or monitoring of the studied indication, not associated with any deterioration in condition
  - Elective or pre-planned treatment for a pre-existing condition that is unrelated to the indication under study and has not worsened since the start of study drug
  - Treatment on an emergency outpatient basis for an event not fulfilling any of the definitions of an SAE given above and not resulting in hospital admission
  - Social reasons and respite care in the absence of any deterioration in the subject's general condition
- Is medically significant (i.e., defined as an event that jeopardizes the subject or may require medical or surgical intervention)

Life-threatening in the context of an SAE refers to a reaction in which the subject was at risk of death at the time of the reaction; it does not refer to a reaction that hypothetically might have caused death if more severe.

Any suspected transmission of an infectious agent via a medicinal product is also considered an SAE.

Medical and scientific judgment should be exercised in deciding whether other situations should be considered serious, such as important medical events that might not be immediately life-threatening or result in death or hospitalization but might jeopardize the subject or might require intervention to prevent one of the other outcomes listed above. Examples of such events are intensive treatment in an emergency room or at home for allergic bronchospasm, blood dyscrasias, or convulsions that do not result in hospitalization.

Serious adverse events are to be monitored continuously and have special reporting requirements (see [Section 11.5](#)). All SAEs will be followed until resolution, stabilization, or until it is judged to be permanent.

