associated with severe sickle cell crises and death in patients with SCD or trait. Licensed in the US since 2008, plerixafor (Mozobil®, Genzyme) is a small molecule, reversible antagonist of chemokine receptor 4 (CXCR4), currently indicated to be used in combination with G-CSF to mobilize HSCs to the peripheral blood for collection and subsequent autologous transplantation in patients with multiple myeloma and non-Hodgkin's lymphoma. Plerixafor acts by disrupting binding to the receptor's cognate ligand, stromal-derived factor-1α (SDF-1α) chemokine ligand 12 (CXCL12), thereby resulting in mobilization of CD34+ HSCs into the peripheral blood. More recently, plerixafor alone has demonstrated efficacy in the mobilization of sufficient HSC for collection in patient populations, including SCD. However, as many as 75% of patients with SCD require 2 or more cycles of multi-day plerixafor administration and apheresis in order to collect sufficient HSCs for genetic modification and infusion, and vaso-occlusive crisis remains a risk with each mobilization and apheresis procedure, with approximately 30% of plerixafor-mobilized patients reported to have experienced VOEs of at least Grade 3 severity during and after harvesting, and approximately 20% of patients reported to have experienced serious vaso-occlusive pain within 2 days post-procedure. Hypomagnesemia, hypokalemia, and hypocalcemia have also been reported commonly among patients with SCD mobilized with plerixafor, although most events were Grade 1 or 2 in severity. Approximately half of patients with SCD require opioid medications within a week prior or subsequent to mobilization and apheresis. Nonetheless, mobilization with plerixafor seems to result in an apheresis product superior to bone marrow harvest, based on the concentration of high-quality CD34+ HSCs most suitable for *ex vivo* manipulation and autologous transplantation.

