**Table 4: Part A Objectives and Endpoints**

Part A Primary Objectives	Part A Primary Endpoints
To characterize the efficacy of a single dose of MGTA-145 and plerixafor for HSC mobilization and apheresis collection in patients with SCD	
 
Determination of the yield of CD34+ cells (CD34+ cells/kg) after 1 dose of MGTA-145 and plerixafor followed by apheresis
 

To characterize the safety and tolerability of MGTA-145 in patients with SCD	
 
Incidence of TEAEs, including drug-related TEAEs, <math>\geq</math>Grade 3 TEAEs, TESAEs, and TEAEs leading to study drug discontinuation
 
Incidence of treatment-emergent <math>\geq</math>Grade 3 clinical laboratory abnormalities
 
Clinically significant changes from baseline in vital signs and laboratory parameters (e.g., serum chemistry, hematology)
 

To measure the mobilization effects of single-day dosing with MGTA-145 and plerixafor in the peripheral blood in patients with SCD	
 
Determination of peak peripheral blood CD34+ counts
 

To characterize the PK profile of MGTA-145 in patients with SCD	
 
Determination of PK exposures
 

To characterize the immunogenicity of MGTA-145 in patients with SCD	
 
Presence and titers of anti-drug antibodies
 

Part A Exploratory Objectives	Part A Exploratory Endpoints
To characterize the phenotype and function of cells collected by apheresis in patients with SCD	
 
Flow cytometric characterization of cells collected following MGTA-145 and plerixafor mobilization and apheresis
 
Characterization of hematopoietic cell function by mouse engraftment studies and/or colony formation assays
 

To assess gene-modifying potential of mobilized CD34 + cells in patients with SCD	
 
Assessment of ability to select and gene-modify CD34+ cells
 

HSC=hematopoietic stem cells; PD=pharmacodynamic(s); PK=pharmacokinetic(s); SCD=sickle cell disease; TEAE=treatment-emergent adverse event; TESAE=treatment-emergent serious adverse event	

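### Section 11.2.4 sets two different thresholds for a medically significant SAE; the looser one, read literally, makes any treated new or worsened event serious and inflates TESAE incidence, a primary safety endpoint

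*Protocol*

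**What the plan says.** Protocol Section 11.2.4 defines an SAE as the appearance or worsening of a sign, symptom or condition "which meets any one of the following criteria". The last listed criterion is: "Is medically significant (i.e., defined as an event that jeopardizes the subject or may require medical or surgical intervention". The parenthesis ends there, with no further condition.

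A later paragraph in the section asks for medical and scientific judgment on whether other situations are serious. It describes important medical events that "might jeopardize the subject or might require intervention to prevent one of the other outcomes listed above". Its illustrations are demanding: "Examples of such events are intensive treatment in an emergency room or at home for allergic bronchospasm, blood dyscrasias, or convulsions".

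Table 4 (Part A) includes among the primary safety endpoints the incidence of "TESAEs, and TEAEs leading to study drug discontinuation"; Table 5 (Part B) and the synopsis say the same. Section 11.5 requires every SAE to be reported within 24 hours, and Section 11.2.4 requires all SAEs to be followed until they resolve, stabilize or are judged permanent.

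**The concern.** The two wordings set the bar at different heights. Under the criterion, possible need for treatment is enough. Under the paragraph, the treatment must be needed to avert a listed serious outcome. The gap between them is the large middle ground of events that are treated but not threatening.

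That middle ground is well populated in this trial. Section 4 describes plerixafor-mobilized patients with sickle cell disease as commonly having low magnesium, potassium or calcium, mostly Grade 1 or 2, and says "Approximately half of patients with SCD require opioid medications within a week prior or subsequent to mobilization and apheresis". Seriousness is decided by the investigator at the site, at about 3 centers, so inconsistent classification cannot be repaired at the analysis stage. At stake are a primary safety endpoint reported without a control arm, and the set of events sent through expedited reporting.

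**Working it through.** The protocol states no figure for this point, so the check is of the text, followed by simple arithmetic for scale.

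**Step 1: the two tests side by side.**

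- Criterion: the event jeopardizes the subject, or may require medical or surgical intervention. Introduced by an i.e. and the word defined, the parenthesis is the operative definition.
- Paragraph: the event might jeopardize the subject, or might require intervention that prevents another listed outcome.

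The main difference is the missing qualifier on intervention. There is also a small one on jeopardy: the criterion requires that the event does jeopardize, the paragraph only that it might.

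**Step 2: apply both to plausible events.**

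| Event | Criterion, read literally | Paragraph |
|---|---|---|
| New pain after dosing, medicated, no jeopardy, no admission | SAE | Not an SAE |
| New Grade 1 low potassium, supplemented, nothing listed to prevent | SAE | Not an SAE |
| Convulsion treated intensively in an emergency room, not admitted | SAE | SAE |
| Brief infusion-related back pain needing no therapy (the usual Phase 1 picture, Table 2 footnote) | Not an SAE | Not an SAE |
| Unchanged baseline pain on the same medication | Not an SAE (no appearance or worsening) | Not an SAE |

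The tests disagree on the first two rows.

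**Step 3: compare with the AE threshold.** Section 11.2.2 makes an abnormal laboratory value an AE if, among other grounds, it needs therapy or medical intervention. The Section 11.2.4 criterion uses nearly the same condition for seriousness. Read literally, a new or worsened laboratory AE that qualifies on that ground is automatically an SAE, so the boundary between AE and SAE disappears for those events.

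**Step 4: scale of one reclassified subject.** Inputs are the minimum evaluable numbers in Section 12.5: 7 in Part A and 3 in Part B. The shift in incidence is 1/n.

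- Part A: 1/7 = 14.3 percentage points.
- Part B: 1/3 = 33.3 percentage points.

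If the second Part A cohort instead enrolls 7 subjects at a lower dose, Part A has 4 + 7 = 11 subjects and the shift is 1/11 = 9.1 points over the whole Part. By dose group, which Section 12.4.1 uses, it is 1/4 = 25 points or 1/7 = 14.3 points. TESAE incidence uses the safety set, which may exceed the evaluable minimum; each shift then shrinks accordingly.

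**Step 5: what is not touched.** The stopping rules in Section 6.6 use CTCAE grade and, for events other than VOE, drug-relatedness; they do not use seriousness. CD34+ yield does not depend on SAE classification.

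**The case against.** The strongest reply is that the wordings need not collide. One criterion suffices, so on a strict reading the criterion decides alone and the paragraph, which addresses other situations, adds little. An experienced investigator would take the paragraph's examples as showing the intended level. The looser wording errs toward over-reporting, the study tests no hypothesis, TESAE incidence sits beside Grade 3 or higher TEAEs that do not depend on seriousness, and with so few subjects each listed SAE can be read individually. All SAEs go to one safety vendor, and the SAE form instructions are not among the documents.

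Most of this stands as a limit on consequence. It does not remove the defect: the strict reading makes the paragraph's qualifier idle and gives the inflated count, the sensible reading departs from the stated definition, and the protocol does not choose. That sites would actually differ is a possibility the text leaves open, not something the documents show.

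Two stronger readings are tempting and are not supported.

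- A reader might infer that the criterion contradicts the exception "Treatment on an emergency outpatient basis for an event not fulfilling any of the definitions of an SAE given above". That exception is a sub-item of the hospitalization criterion. It says only that such treatment does not count as hospitalization; an event can fail that criterion and still meet another.
- A reader might measure the gap from Section 4: half of 10 subjects needing opioids (0.50 × 10 = 5) against "approximately 20% of patients reported to have experienced serious vaso-occlusive pain within 2 days post-procedure" (0.20 × 10 = 2). The opioid share includes use before the procedure, and the post-procedure part is not given. The 20% is not shown to follow the narrower definition, and its time window differs. The two figures do not measure the two tests.

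**Conclusion.** The point holds as an inconsistency in a definition that gives a wrong count if its criterion is followed as written. Section 11.2.4 has two thresholds for medical significance and no rule for choosing between them. The looser one classifies any treated new or worsened event as serious, inflating TESAE incidence and the 24-hour reporting load.

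How many events would be affected cannot be worked out from the documents. The only defensible scale is the effect of one reclassified subject: about 14 percentage points in Part A and 33 in Part B, assuming safety sets of 7 and 3. The exposure lies mainly in treated VOE, other treated pain and corrected laboratory values. A reader might also infer a threat to dose progression or to the efficacy result; neither follows, because the stopping rules and CD34+ yield do not use seriousness. The correction should be made because it is specific and nearly free, not because the study's main conclusions hang on it.

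**What to change.** In Section 11.2.4, reword the last criterion to match the paragraph: an important medical event that may jeopardize the subject, or may require intervention to prevent one of the other listed outcomes. This settles both the intervention limb and the jeopardy limb. Use that single test in the SAE form instructions and as the basis for the TESAE endpoint in both Parts.

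The cost is one sentence in the next amendment and a matching line on the SAE form. No data are lost: treated events that are not serious are still recorded and graded as AEs. If SAEs have already been reported under the present wording, check their stated seriousness criterion once, so that all subjects are counted on the same basis.

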#### 11.3. Relationship to Study Drug

An Investigator who is qualified in medicine must make the determination of relationship to the investigational product for each AE/SAE (related or unrelated). The Investigator should decide

whether, in his or her medical judgment, there is a reasonable possibility that the event may have been caused by the investigational product. If no valid reason exists for suggesting a relationship, then the AE/SAE should be classified as “unrelated.” If there is any valid reason, even if undetermined, for suspecting a possible cause-and-effect relationship between the investigational product and the occurrence of the AE/SAE, then the AE/SAE should be considered “related.”

For the purpose of regulatory reporting requirements, causal relationships of definite, probable, and possible will be considered treatment related, while unlikely and not related will be considered not treatment related.

#### **11.4. Recording Adverse Events**

In the event that a subject experiences an AE or SAE, an assessment of the event will be performed at the study site at the time of the incident and recorded on the AE eCRF page. If the subject is not evaluated at the study site at the time of the AE/ SAE, every effort will be made to obtain safety assessment data from the subject’s local treating physician. If a subject is prematurely discontinued from study procedures, only safety data considered relevant for the assessment of the MGTA-145 safety profile will be collected in the clinical database.

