**Figure 1: Part A (Single Dose) and Part B (Single Dose on 2 Consecutive Days)**

**Table 6: Schedule of Assessments: Part A (Single Dose)**

Study Period Procedures	Screening	Baseline	Mobilization /Apheresis	1-week follow-up (Day 7 to 10) b	End of Study (Day 30) b
	Day -30 to -2	Day -1	Day 1		
Informed consent	X				
Medical history	X	X			
Inclusion/exclusion criteria review	X				
Height		X			
Weight		X		X	
Physical examination	X	X		X	
Symptom-directed physical examination			X		
Vital signs a	X	X	X	X	
Serology c	X				
Serum or urine $\beta$ -hCG (females)	X	X			
12-lead ECG	X				
Urinalysis		X	X	X	
Chemistry d	X	X	X	X	
Hematology e	X	X	X	X	
Anti-drug antibodies		X		X	
Plerixafor administration			X		
MGTA-145 administration f			X		
Apheresis procedure			X		
Apheresis yield g			X		
PROMIS and ASCQ-Me questionnaires h			X	X	
Non-serious AEs and SAEs i	X	X	X	X	X j
Concomitant medications	X	X	X	X	X j

AE=adverse event; ASCQ-Me=Adult Sickle Cell Quality of Life Measurement Information; BPI=Brief Pain Inventory;  $\beta$ -hCG=beta-human chorionic gonadotropin; CFU= colony-forming unit; ECG=electrocardiogram; PK=pharmacokinetics; NRS=Numeric Rating Scale; SAE=serious adverse event

a Vital sign measurements will be taken in the sitting position after the subject has been resting for 5 minutes. Vital signs should be taken before any blood samples are drawn.

b If a subject does not complete dosing, there will not be follow-up visits. If a subject received MGTA-145 but did not complete apheresis, then follow-up visits are required.

c All subjects enrolled in Parts A will be screened for human immunodeficiency virus (HIV), hepatitis B surface antigen (HBsAg), human T-cell leukemia virus (HTLV), and hepatitis C virus (HCV) at the screening visit. Subjects who are HCV antibody positive must have a HCV ribonucleic acid (RNA) polymerase chain reaction (PCR) test.

d Clinical chemistry consists of sodium, potassium, chloride, bicarbonate, blood urea nitrogen, creatinine, glucose, calcium, aspartate aminotransferase (AST), alanine aminotransferase (ALT), alkaline phosphatase, albumin, total and indirect bilirubin. Clinical chemistry sample collection should be done prior to dosing on Day 1. All other clinical chemistry sample collections will be done on the morning of the assessment day.

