### 7.3. Subject Withdrawal Criteria

A subject may be discontinued from the study procedures at the discretion of the Investigator. In such a case, the decision to discontinue the subject will be made by the Investigator in consultation with the study Medical Monitor. Subjects may voluntarily withdraw consent to participate in the study for any reason at any time. Withdrawal of consent occurs when a subject:

- Does not want to continue participation in the study
- Does not want any further study visits or assessments
- Does not want any further study-related contacts

Subjects who discontinue study procedures should not be considered withdrawn from the study unless they withdraw their consent. If a subject withdraws consent, the Investigator must make every effort (e.g., telephone, email, letter) to determine the primary reason for this decision and record this information in the electronic case report form (eCRF). If the subject is willing to

perform end-of-study assessments, these should be conducted. Otherwise, no further assessments should be conducted. All biological material that has not been analyzed at the time of withdrawal must not be used unless written consent is obtained. Further attempts to contact the subject are not allowed unless safety findings require communication or follow-up.

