## 11. ASSESSMENT OF SAFETY

Subject safety will be assessed based on monitoring of AEs, vital signs, physical examinations, clinical laboratory evaluations, and development of anti-drug antibodies. Adverse events will be graded using the NCI CTCAE version 5.0.

Vaso-occlusive events are known to be associated with plerixafor use in patients with SCD undergoing mobilization and apheresis, reaching Grade 3 or higher severity in approximately 30% of patients. During each planned post-cohort assessment, the DMC is to evaluate and recommend whether to proceed to the subsequent cohort at the current dosing regimen based on evaluation of safety, PK, and mobilization kinetics. At each assessment, the number and proportion of patients reporting VOEs within approximately one week (1-week follow-up visit, occurring 7 to 10 days) after MGTA-145 dosing will be determined, and the DMC will determine whether a stopping rule has been met (Section 6.6), in which case no further dosing at that dosing regimen will take place unless the DMC determines that it is safe to do so. Pain occurring during the infusion or immediately after infusion and resolving within 1 hour of infusion will not be considered VOE and will not count toward the stopping rule.

In Part B, if a subject has a VOE following the first MGTA-145 infusion, proceeding to the second infusion will be at the Investigator's discretion.

As described below in Section 6.6, the occurrence of a Grade  $\geq 4$  VOE in any subject within approximately one week (1-week follow-up visit, occurring 7 to 10 days) after MGTA-145 dosing will be considered a stopping rule.

Excluding VOE, if any subject develops a Grade 3 or higher drug-related TEAE, based on the NCI CTCAE version 5.0, dosing of the current cohort will not be continued until the DMC assesses whether dosing may continue and whether dosing modifications are needed. In addition to VOEs, Grade 3 AEs known to be associated with plerixafor (i.e., nausea, vomiting, diarrhea, headache [as per plerixafor label]) or MGTA-145 (i.e., bone pain that is less than 1 hour in duration from the time the bone pain is first reported) will not count toward this stopping rule.

Pre-medications will be at the discretion of the Principal Investigator according to institutional or center standard for apheresis collection. All subjects will have adequate hydration before and during the apheresis procedure.

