### **11.2. Adverse Events and Serious Adverse Events**

#### **11.2.1. Adverse Events**

Collection of non-serious AEs and serious adverse events (SAEs) will begin once the ICF is signed and continue until the EOS visit. Non-serious AEs and SAE reporting will end at the EOS visit. Any SAE occurring after the reporting period must be promptly reported if a causal relationship to study drugs is suspected.

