#### **11.2.2. Adverse Event Definition**

An AE is any untoward medical occurrence (i.e., any unfavorable and unintended sign [including abnormal laboratory findings], symptom, or disease) in a subject or clinical investigation subject administered a medicinal product. Therefore, an AE may or may not be temporally or causally associated with the use of a medicinal (investigational) product.

The occurrence of AEs should be sought by non-directive questioning of the subject at each visit during the study. Adverse events also may be detected when they are suspected by the subject or subject's family during or between visits or through physical examination, laboratory test, or other assessments.

Abnormal laboratory values or test results constitute AEs only if they fulfill at least one of the following criteria:

- Induce clinical signs or symptoms
- Are considered clinically significant
- Require therapy or medical intervention

Clinically significant abnormal laboratory values or test results should be identified through a review of values outside of normal ranges/clinically notable ranges, significant changes from baseline values or the previous visit, or values which are considered to be non-typical in subjects with underlying disease. Investigators have the responsibility for managing the safety of individual subjects and identifying and documenting AEs.

From the signing of informed consent, non-serious AEs and SAEs must be recorded on the AE eCRF for subjects who enroll in the study. The Investigator should attempt to establish a diagnosis of the event based on signs, symptoms and/or other clinical information. In such cases, the diagnosis should be documented as the AE and/or SAE rather than as the individual signs/symptoms. The AEs should be accompanied by the following information:

1. The CTCAE Grade (version 5.0)

If CTCAE grading does not exist for an AE (and this is rare), use:

Grade 1=mild

Grade 2=moderate

Grade 3=severe

Grade 4=life-threatening

Grade 5- death

2. Relationship to the study treatments (definitely related, probably related, possibly related, unlikely related, not related).
3. Duration (start and end dates) or if the event is ongoing an outcome of not recovered/not resolved should be reported.
4. Whether it constitutes an SAE (see [Section 11.2.4](#) for the definition of SAE).
5. Action taken regarding study treatments.

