#### **11.5. Reporting Serious Adverse Events**

To ensure subject safety, every SAE occurring after the subject has provided informed consent, through the end of the study, regardless of causality, must be reported to Premier within 24 hours of learning of its occurrence. Drug-related SAEs reported to the study site after the EOS visit should also be reported to Premier.

Recurrent episodes, complications, or progression of the initial SAE must be reported as follow-up to the original episode, regardless of when the event occurs. This report must be submitted within 24 hours of the Investigator receiving the follow-up information. An SAE that is considered completely unrelated to a previously reported one should be reported separately as a new event.

In addition, SAEs (initial and follow-up) must be reported to Premier **within 24 hours of awareness** of the SAE or changes to an existing SAE. This should be done by emailing or faxing a signed copy of the **SAE Report Form** using the contact details below.

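### Section 11.4 lets adverse events after early discontinuation be left out of the clinical database, against the rest of the protocol, so TEAE incidence could be understated

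*Protocol*

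**What the plan says.** The last sentence of Section 11.4 applies to a subject who is prematurely discontinued from study procedures. For that subject, "only safety data considered relevant for the assessment of the MGTA-145 safety profile will be collected in the clinical database". The section does not say who decides relevance, by what criterion, or for which period. Its opening sentence requires each adverse event to be assessed at the site when it happens and entered on the AE page of the eCRF.

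Elsewhere the protocol makes no exception for such a subject:

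- Section 11.2.1: "Collection of non-serious AEs and serious adverse events (SAEs) will begin once the ICF is signed and continue until the EOS visit".
- Section 11.2.2: "From the signing of informed consent, non-serious AEs and SAEs must be recorded on the AE eCRF for subjects who enroll in the study".
- Section 7.3: "Subjects who discontinue study procedures should not be considered withdrawn from the study unless they withdraw their consent".
- Table 6, footnote b, repeated as footnote c of Table 7: "If a subject received MGTA-145 but did not complete apheresis, then follow-up visits are required". Both tables schedule adverse event collection at those visits.
- Section 11.5, with a 24-hour deadline: "every SAE occurring after the subject has provided informed consent, through the end of the study, regardless of causality, must be reported to Premier".

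The primary safety endpoint in Table 4 begins "Incidence of TEAEs, including drug-related TEAEs", so related events are a subset of what is counted. Table 5 says the same for Part B. Section 12.1 defines the safety set as enrolled subjects who received a dose of MGTA-145.

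**The concern.** A site cannot follow both Section 11.4 and the other sections for the same subject. The relevance filter acts only on subjects who stopped early, in an open-label study without a control arm, and whoever applies it knows the treatment. Those subjects stay in the safety denominator, so any filtering can only lower the reported incidence. No analysis plan can recover events that were never entered.

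The filter is tied to MGTA-145, whereas every subject also receives plerixafor and is scheduled for apheresis. An event put down to either of these, or to the underlying disease, could be judged outside the MGTA-145 profile although it belongs in the endpoint. Vaso-occlusive events (VOEs) are one possible case. Section 11 states that "Vaso-occlusive events are known to be associated with plerixafor use in patients with SCD undergoing mobilization and apheresis", while the cohort stopping rules in Section 6.6.1 count Grade 3 VOEs without asking about relationship.

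**Working it through.** **1. The passages side by side, for a subject who received MGTA-145 and then stopped procedures**

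| Question | Section 11.4 | Other sections |
|---|---|---|
| Still in the study? | Not addressed | Yes, unless consent is withdrawn (7.3) |
| Which events are recorded? | Those judged relevant to MGTA-145 | All, serious and non-serious (11.2.1, 11.2.2) |
| Until when? | Not stated | End-of-study contact (11.2.1) |
| In the TEAE denominator? | Not addressed | Yes (12.1) |
| Which events count for the endpoint? | Not addressed | All TEAEs (Tables 4 and 5) |

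**2. Effect on TEAE incidence**

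If one subject's only event in a category is not entered, incidence in that category falls by 1/n:

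- Part A, n = 11 (upper planned size): 1/11 = 9.1 points
- Part A, n = 7 (lower planned size): 1/7 = 14.3 points
- A dose group of 4, if only the first cohort receives 0.03 mg/kg: 1/4 = 25 points
- Part B, n = 3: 1/3 = 33.3 points

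The shift is zero in any category where the subject already has a recorded event. For TEAEs overall this will often be so. Table 2 reports drug-related TEAEs in 75.0% to 88.9% of Phase 1 subjects given the combination.

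**3. Effect on the stopping rules**

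Inputs: the rules are met at 3 or more of 4 (Section 6.6.1.1) and at 4 or more of 7 (Section 6.6.1.2), with an assumed rate of 30% under plerixafor alone.

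The plan's own figures, from the binomial upper tail, reproduce:

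- P(X ≥ 3; n = 4, p = 0.30) = 8.37%
- P(X ≥ 4; n = 7, p = 0.30) = 12.60%

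Now suppose one subject's Grade 3 VOE occurred and was not recorded. The assessment changes only if the other subjects bring the count to one below the threshold:

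- First cohort, exactly 2 of the other 3: 3 × p² × (1 − p). At p = 0.30 this is 3 × 0.09 × 0.70 = 18.9%.
- All 7 subjects, exactly 3 of the other 6: 20 × p³ × (1 − p)³. At p = 0.30 this is 20 × 0.027 × 0.343 = 18.5%.

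| True rate | Changed, 4 subjects | Changed, 7 subjects |
|---|---|---|
| 20% | 9.6% | 8.2% |
| 30% | 18.9% | 18.5% |
| 40% | 28.8% | 27.6% |

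The same loss can be expressed as a trigger probability. If one subject's VOE, should it occur, cannot be counted, the first rule needs 3 of the other 3 and the second needs 4 of the other 6. At 30% the probabilities fall from 8.37% to 2.70% and from 12.60% to 7.05%. The first drop, 5.67 points, equals 0.30 × 18.9%.

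These figures assume that one such subject exists, that subjects share one rate and are independent, and that the subject is not replaced. The documents do not give the chance of an omission.

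**The case against.** The strongest reply is that Section 11.4 never orders an event to be dropped. It can be read as limiting collection after discontinuation to safety data, as opposed to pharmacodynamic samples or questionnaires, and it speaks of relevance, not relatedness. That reading is possible. Even so, the sentence qualifies which safety data are collected, and it leaves the choice to an unnamed person.

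A reader might go further and infer that Section 11.4 removes VOEs from the stopping count. The documents do not support that, for these reasons:

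- A VOE that leads to discontinuation comes before it, and the opening sentence of Section 11.4 has it recorded.
- Section 6.6.1 builds the stopping rules to detect VOEs in excess of plerixafor alone, which makes a VOE relevant to MGTA-145 on the protocol's own terms.
- Subjects are observed on site until at least one day after the last apheresis (Section 6.3), so the exposed events are mainly later ones.
- Serious VOEs go to the safety vendor whatever their cause (Section 11.5).
- No section confines the DMC's count to the clinical database. Section 6.6.1.2 also lets the DMC halt progression on all available data.

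A reader might also infer that one missed event is decisive. It is so only when the true count is exactly at the threshold. In addition, Section 12.5 allows further enrolment to reach 4 and 7 evaluable subjects.

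All of this limits the VOE route. It leaves the contradiction and the TEAE route standing. Vendor reporting does not cover non-serious events, and it does not put serious ones into the clinical database.

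**Conclusion.** This is an internal inconsistency that should be corrected. Section 11.4 permits, without requiring, that events after discontinuation be left out of the clinical database. These would mainly be non-serious events, in subjects who remain in the study and in the safety set. TEAE incidence could then be understated, by 9 to 14 points per subject in Part A and 33 in Part B, in categories where that subject has no other recorded event. How many subjects would be affected is unknown.

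The effect on stopping is secondary. It requires a later-onset, unrecorded Grade 3 VOE and a count exactly at the threshold, which has a probability of about 19% at a 30% rate and about 8% to 29% over rates of 20% to 40%, given that an omission occurs. The text does not support saying that the stopping rules fail or that VOEs are excluded. The plan's 8.37% and 12.60% are correct as calculated, and no sample size figure depends on this point.

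**What to change.** Replace the last sentence of Section 11.4 with: *For any subject who received MGTA-145 and stops study procedures early, all AEs and SAEs (including all VOEs) are recorded in the clinical database through the EOS contact regardless of relationship, unless consent is withdrawn.*

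In the same amendment, reconcile the first part of footnote b in Table 6 and footnote c in Table 7 with this sentence. Those footnotes say that a subject who does not complete dosing has no follow-up visits. This could apply to a Part B subject given MGTA-145 on one day only, who is nevertheless in the safety set.

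The change concerns data recording. It costs one sentence, a footnote edit and a few more AE records. For most subjects the visits and the end-of-study call are already scheduled. For incompletely dosed subjects it may add follow-up contacts that the footnotes now omit, depending on how they are reconciled.
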